2.2 Study duration

The start of the study is defined as the first visit for the first participant providing informed consent. Similarly, the end of study (EOS) is defined as the last visit or scheduled procedure shown in the

schedule of assessments for the last participant. Primary study completion is defined as the final date on which data for the primary endpoint are expected to be collected. The study duration is expected to be around 12 months, subject to change on an ongoing basis.

2.3 Study termination

The sponsor reserves the right to terminate any portion of the study at any time. Possible reasons for termination include:

- Safety reasons
- New scientific knowledge becomes known that makes the objectives of the study no longer feasible/valid.
- Unsatisfactory enrolment of participants.

In terminating the study, the sponsor will ensure that adequate consideration is given to the protection of the subjects' interests.

3. Study objectives and endpoints

3.1 Primary objective

We would like to investigate whether irradiation with open face masks and SS, and without masks and SS, for patients with head and neck cancer is at least as good as irradiation with a full thermoplastic mask in terms of set-up and treatment accuracy.

3.2 Primary endpoint

- 1) Set-up and treatment accuracy, determined by in-vivo dosimetry using PerFRACTION, and by the evaluation of intrafractional motion by comparing a CBCT before and at the end of treatment in patients receiving RT with an open mask, without a mask and using a closed thermoplastic mask.
- 2) Average treatment time for the different deliveries (full mask, open mask, without a mask)

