Study objectives and endpoints:	
Primary objective To compare the accuracy and reproducibility of radiation therapy (RT) with open face masks and surface-scanning (SS), and with SS alone without masks to irradiation with a full thermoplastic mask, for patients with head and neck cancer.
 
Primary endpoint Set-up and treatment accuracy, determined by in-vivo dosimetry using PerFRACTION, and by the evaluation of intrafractional motion by comparing a CBCT before and at the end of treatment in patients receiving RT with an open mask, without a mask and using a closed thermoplastic mask.
 
Secondary objectives
 
 1) to demonstrate that irradiation with open face masks and SS or no face masks and SS for patients with head and neck cancer reduces the patients' levels of distress when compared to irradiation with full thermoplastic masks. 2) to demonstrate that irradiation with open face masks and SS or no face masks and SS is feasible for the treating RTT's. 
Secondary endpoints
 
 1) Level of distress of patients, determined by using the subjective units of distress scale (scale of 0-100). 2) Preferred delivery technique as evaluated by treating RTT's involved in this study.
Study design:	Non randomised clinical interventional study
Planned sample size:	In total, 24 patients will be enrolled into this study.

Medical condition or disease under investigation:	Adult HNC patients receiving radiation therapy as their primary treatment

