1.2 Risks and benefits

- **Possible risk:**

A longer treatment time in the open face mask or mask-less phase

- **Possible benefit:**

-Possibly less claustrophobia in the open face mask or mask-less phase

2. Overall study design

The study is designed to evaluate whether irradiating head and neck cancer patients without a mask or with open face masks using SS is comparable to irradiation with full thermoplastic masks in terms of set-up and treatment accuracy and average treatment time.

In total, 24 patients will participate in the study. They are treated with radiotherapy for 35 fractions.

The treatment of every patient will be divided into different phases:

- patients will be irradiated with an open face mask and SS
- patients will be irradiated without a mask but with SS
- patients will be irradiated with a full thermoplastic mask

The delivery technique will change for every patient each 5 fractions.

- The first 8 patients included in the study will have the following schedule:
full mask-open mask-no mask- full mask-open mask-no mask-full mask
- The 9th till 16th patient included in the study will have the following schedule:
open mask-no mask-full mask-open mask-no mask-full mask-open mask
- The 17th till 24th patient included in the study will have the following schedule:
no mask-full mask-open mask- no mask- full mask-open mask-no mask

We chose the number of patients for each group based on the published literature and the power calculation (Table 1).

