2.1 Study period

For each participant, the study starts once written consent is provided and is composed by 2 study phases.

Screening phase

Eligibility of patients will be determined according to the inclusion/exclusion criteria as detailed in section 8. Patients are asked complete the validated Dutch claustrophobia questionnaire before start of treatment (see Section 12 and appendix 1).

Treatment phase

Once enrolled, fully eligible patients will start the intended RT according to the standard of care. The RT dose prescription is left to the discretion of the treating radiation oncologist and is the current standard treatment. Patients are asked about their distress level by the treating physician on a weekly basis (see Section 12 and appendix 2). A score of 0-100 is given by using the Subjective Units of Distress Scale.

The set-up and treatment accuracy will be determined by in-vivo dosimetry using PerFRACTION and by the evaluation of intrafractional motion by comparing a CBCT before and at the end of treatment.

The average treatment time will be measured for all treatment fractions.

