3.4 Secondary endpoints

- 3) Level of distress of patients, determined by using the subjective units of distress scale (scale of 0-100).
- 4) Preferred delivery technique as evaluated by treating RTT's involved in this study.

Our hypothesis for this trial can be best described by the PICO (Patient Intervention Comparison Outcome):

- Patient: patients who are in need of primary treatment with radiotherapy for a histologically confirmed HNC
- Intervention: irradiation with SS and an open face mask; irradiation with SS but without a thermoplastic mask
- Comparison: standard of care treatment, irradiation with a full thermoplastic mask
- Outcome: accuracy of the irradiation (in-vivo dosimetry, intra-fractional motion during radiotherapy); duration of the irradiation in the different groups; results of claustrophobia questionnaires; results of RTT satisfaction questionnaires

4. Study population

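### Treatment time is primary in 3.2 but not in the synopsis or 3.1, and its margin-free paired t-test cannot support the stated comparability aim; dosimetry, also primary, has no analysis in 10.2

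*Combined protocol and SAP*

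**What the plan says.** **Treatment time.** Section 3.2 has two numbered primary endpoints; the second is "Average treatment time for the different deliveries (full mask, open mask, without a mask". The synopsis primary objective is "To compare the accuracy and reproducibility of radiation therapy (RT) with open face masks and surface-scanning (SS", with SS alone and the full mask as the other techniques, and its primary endpoint is accuracy alone. Section 3.1 asks whether the new techniques are such that irradiation "is at least as good as irradiation with a full thermoplastic mask in terms of set-up and treatment accuracy"; time is not mentioned. The secondary endpoints, in the synopsis and in 3.4, are patient distress, "determined by using the subjective units of distress scale (scale of 0-100", and the technologists' preferred technique.

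Time does appear elsewhere. Section 2 asks whether the techniques are "comparable to irradiation with full thermoplastic masks in terms of set-up and treatment accuracy and average treatment time". Section 2.1 says "The average treatment time will be measured for all treatment fractions". The PICO outcomes in 3.4 include "duration of the irradiation in the different groups". Section 1.2 gives one possible risk: "A longer treatment time in the open face mask or mask-less phase".

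**Analysis.** Section 10.2 and the synopsis methods apply paired t-tests to the parameters named just before (mean displacements and their standard deviations, and the population mean, systematic and random errors) and to timing data. No margin, direction or hypothesis is given for time.

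**Dosimetry.** PerFRACTION in-vivo dosimetry is part of the primary accuracy endpoint in the synopsis and in 3.2, and 7.1 schedules it for the first 3 sessions of each phase. Neither 10.2 nor the synopsis methods mentions it.

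**Displacement.** Sections 10.1 and 10.2 both state 24 patients, 95% power, a 2 mm excess in mean displacement to be ruled out, and a one-sided 0.05 level for non-inferiority.

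**The concern.** The documents define two different sets of primary endpoints. Suppose accuracy proves non-inferior but sessions take longer, which is the one risk that 1.2 anticipates. The trial is then positive under the synopsis and 3.1. Under 3.2 its result is undefined, because no rule says what time must show.

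The aim and the test for time also do not match. Section 2 looks for comparability. A t-test against zero difference can show that times differ, but failing to reject zero does not show that they are alike. With 24 patients, a real lengthening could go undetected and be reported as no difference.

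For dosimetry, a component of the primary endpoint could have its variable and summary chosen after the data are seen. For displacement, the margin is stated, but the reader must infer which displacement it covers and how the paired t-test is turned into a test against 2 mm.

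**Working it through.** **1. The plan's own figure.** 24 patients and 95% power cannot be reproduced, because no SD is given. Assuming a true difference of zero and a paired comparison, the normal formula SD = margin × √n / (z₀.₉₅ + z₀.₉₅) gives 2 × √24 / (1.645 + 1.645) = 2.98 mm. The noncentral t version with 23 degrees of freedom gives 2.89 mm. So 24 follows if the SD of the within-patient difference is about 2.9 to 3.0 mm, but the documents do not say so. The figure concerns displacement only; it says nothing about time or dosimetry.

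**2. Status of time, side by side.**

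| Place | Time included? |
|---|---|
| Synopsis, primary objective and endpoint | No |
| Section 2, design aim | Yes, alongside accuracy |
| 3.1, primary objective | No |
| 3.2, primary endpoint | Yes, item 2 |
| Synopsis and 3.4, secondary endpoints | No |
| 3.4, PICO outcomes | Yes, without a status |
| 10.2 and synopsis methods | Paired t-test, no margin |

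**3. What the t-test for time can miss.** Inputs: n = 24 pairs (10.1; the maximum, since 4.3 does not replace withdrawals), 23 degrees of freedom, level 0.05. No SD for time is given, so the true difference is expressed as δ, in units of the SD of the within-patient differences. The noncentrality is δ√24. The critical value is 2.069 two-sided or 1.714 one-sided. The probability of a non-significant result is the noncentral t probability below the critical value (between ± the critical value when two-sided).

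| δ | δ√24 | Two-sided 0.05 | One-sided 0.05 |
|---|---|---|---|
| 0.3 | 1.47 | 71% | 59% |
| 0.4 | 1.96 | 53% | 40% |
| 0.5 | 2.45 | 35% | 23% |

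Both columns are shown because the plan gives no sidedness for time; its one-sided wording is tied to the 2 mm displacement margin.

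**4. What an interval would show.** The half-width of a two-sided 95% confidence interval is 2.069 / √24 = 0.42 SD, so the interval shows directly which differences are still possible. If time were tested for non-inferiority at one-sided 0.05 with a true difference of zero, 24 pairs would need a margin of about 0.52, 0.62 or 0.69 SD for 80%, 90% or 95% power.

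**5. Dosimetry.** The t-tests in 10.2 cover the parameters listed before them, and all of these are displacement quantities. The accuracy row of the synopsis names PerFRACTION as a measurement but gives no variable, per-patient summary, criterion or test. If a phase means each block of 5 fractions, the schedule yields 7 × 3 = 21 measured sessions per patient, at most 21 × 24 = 504. If it means each technique, it yields 3 × 3 = 9 per patient, at most 216.

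**6. Displacement.** Section 10.2 contains the margin, the level and the one-sided non-inferiority intent. It does not say whether the margin applies per axis or to a 3D vector, or to set-up or intrafraction motion. It also does not state the step that compares a confidence limit with 2 mm.

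**The case against.** Several points on the other side stand.

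- A reader might infer that the plan has no non-inferiority test for displacement. It does not say that: 10.2 itself gives the margin, level, direction and framework. Only the explicit confidence-limit step and the identity of the displacement are missing.
- A reader might infer that a paired t-test is the wrong tool for time. It is not: with a margin set in advance, the same paired framework would serve non-inferiority or equivalence. The gap is the missing margin and hypothesis. A difference test is also reasonable for detecting longer sessions.
- A reader might infer that the sponsor intends to read a non-significant result as comparability. No section says so. The comparability wording for time occurs once, in section 2, and 3.1 limits its claim to accuracy.
- A reader might infer that time was meant to be secondary. The body numbers its endpoints 1 to 4 across 3.2 and 3.4 with time as item 2, which suggests deliberate placement; the synopsis may be what needs updating.
- A reader might infer that PerFRACTION is specified nowhere. Workflow detail in 6.1 is not visible in the text supplied, so the point is confined to 10.2 and the synopsis methods.

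None of this removes the contradiction over the status of time or supplies an analysis that matches the aim in section 2.

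**Conclusion.** The point holds, as something the sponsor should correct. The conflict over the primary endpoint set is plain from the text and needs no calculation. The planned test of time cannot support comparability as it stands: differences of 0.3 to 0.5 SD would be missed in 71% to 35% of trials two-sided, or 59% to 23% one-sided. These figures assume 24 complete pairs and normally distributed within-patient differences. They cannot be put into minutes, because the documents give no SD for time.

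The missing dosimetry analysis in 10.2 and the synopsis methods is real, though taken alone it is largely missing detail. For displacement, the finding is limited to a stated non-inferiority test that is not fully spelled out.

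**What to change.** 1. Give treatment time one status, primary or secondary at the sponsor's choice, and carry it through the synopsis, section 2, 3.1 to 3.4 and 10.2. In either case, report the within-patient difference from full mask (per-patient mean by technique) with a 95% confidence interval for each of the other two techniques, and state that a non-significant t-test is not read as comparability. If time stays primary, add a justified margin.
2. In 10.2 and the synopsis methods, state before the data are seen whether dosimetry is confirmatory, with a criterion, or supporting. Name the PerFRACTION variable, and report within-patient differences from full mask with 95% confidence intervals.
3. In 10.2, name the displacement to which the 2 mm margin applies. Make the stated test explicit: compare the one-sided 95% upper confidence limit of the within-patient difference from full mask with 2 mm.

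Cost: wording and analysis only, with no extra patients, sessions or imaging. If time becomes secondary it loses its primary label, and if dosimetry becomes supporting it loses its confirmatory role. Keeping either one means justifying a margin or criterion.

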3.3 Secondary objective

Our secondary objective is:

- 3) to demonstrate that irradiation with open face masks and SS or no face masks and SS for patients with head and neck cancer reduces the patients' levels of distress when compared to irradiation with full thermoplastic masks.
- 4) to demonstrate that irradiation with open face masks and SS or no face masks and SS is feasible for the treating RTT's.

3.4 Secondary endpoints

- 3) Level of distress of patients, determined by using the subjective units of distress scale (scale of 0-100).
- 4) Preferred delivery technique as evaluated by treating RTT's involved in this study.

Our hypothesis for this trial can be best described by the PICO (Patient Intervention Comparison Outcome):

- Patient: patients who are in need of primary treatment with radiotherapy for a histologically confirmed HNC
- Intervention: irradiation with SS and an open face mask; irradiation with SS but without a thermoplastic mask
- Comparison: standard of care treatment, irradiation with a full thermoplastic mask
- Outcome: accuracy of the irradiation (in-vivo dosimetry, intra-fractional motion during radiotherapy); duration of the irradiation in the different groups; results of claustrophobia questionnaires; results of RTT satisfaction questionnaires

4. Study population

4.1 Subject inclusion criteria

Each potential subject must satisfy all of the following criteria to be enrolled in the study.

- Patients ≥ 18 years old
- Histologically confirmed head and neck cancer.
- Patients treated with RT as primary treatment.
- An Eastern Cooperative Oncology Group (ECOG) Performance Status grade of 0-1 as defined in Appendix 3.
- Each subject must sign an informed consent form (ICF) indicating that he understands the purpose of and procedures required for the study and is willing to participate in the study.
- Patients must be willing to comply with treatment plan and other study procedures.

4.2 Subject exclusion criteria

Each potential subject must NOT satisfy any of the following criteria to be enrolled in the study.

- Patients with significantly altered mental status or with psychological, familial, sociological or geographical condition potentially hampering compliance with the study.
- Patients who cannot stay still during fraction because of a disorder (e.g. Parkinson's disease)

4.3 Subject withdrawal criteria and procedures

- The general condition of the patient is too bad to continue the RT
- The patient can withdraw from the study at any moment for any reason

The patients who withdraw will not be replaced.

Specific aftercare for this therapeutic strategy is no different from the current standard of care.

5. Treatment allocation

Patients will be assigned to a study group based on their date of enrolment.

The treatment of every patient will be divided into different phases:

- patients will be irradiated with an open face mask and SS
- patients will be irradiated without a mask but with SS
- patients will be irradiated with a full thermoplastic mask

The delivery technique will change for every patient each 5 fractions.

[figure not shown]
- The first 8 patients included in the study will have the following schedule:
full mask-open mask-no mask- full mask-open mask-no mask-full mask
- The 9th till 16th patient included in the study will have the following schedule:
open mask-no mask-full mask-open mask-no mask-full mask-open mask
- The 17th till 24th patient included in the study will have the following schedule:
no mask-full mask-open mask- no mask- full mask-open mask-no mask

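### The three technique orders are filled in consecutive blocks of eight by enrolment date, so technique is balanced over treatment phase only if all 24 patients complete; permuted blocks of three would protect a shortened study at little cost

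*Combined protocol and SAP*

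**What the plan says.** Section 5 (Treatment allocation) states: "Patients will be assigned to a study group based on their date of enrolment". Sections 2 and 5 and the synopsis then fix the order by enrolment rank, beginning with "The first 8 patients included in the study will have the following schedule". Section 5 gives the three orders in full:

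- Patients 1-8: "full mask-open mask-no mask- full mask-open mask-no mask-full mask"
- Patients 9-16: "open mask-no mask-full mask-open mask-no mask-full mask-open mask"
- Patients 17-24: "no mask-full mask-open mask- no mask- full mask-open mask-no mask"

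The synopsis describes the design as "Non randomised clinical interventional study". Section 2.3 lists "Unsatisfactory enrolment of participants" among the reasons for termination, and section 4.3 adds: "The patients who withdraw will not be replaced". Section 10.2 plans paired t-tests for displacement and timing and summary scores for the questionnaires. It names no term for treatment phase, order or calendar time.

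**The concern.** Three rotated orders are a sensible way to keep week-of-treatment effects out of the technique comparison. The protection depends on having equal numbers in each order. Because the orders are filled one after another, equality is reached only at patient 24: no patient starts with the open mask before patient 9, and none starts without a mask before patient 17. A study closed early would have an incomplete set of orders.

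The endpoints are of a kind that can change over a course. Distress and set-up time may be higher in the first week, when everything is unfamiliar. Section 1.1 notes that masks do not adapt to weight loss or edema, so accuracy may drift. With an unbalanced set of orders, such changes would be read as technique differences. Consecutive filling also means that a difference between orders cannot be told apart from a change over calendar time, such as growing staff experience with surface scanning.

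**Working it through.** **Inputs from the documents.** There are 35 fractions in phases of 5 (section 2), so 35/5 = 7 phases. Write F for full mask, O for open mask and N for no mask.

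| Order | F phases (mean) | O phases (mean) | N phases (mean) |
|---|---|---|---|
| A, patients 1-8 | 1, 4, 7 (4.0) | 2, 5 (3.5) | 3, 6 (4.5) |
| B, patients 9-16 | 3, 6 (4.5) | 1, 4, 7 (4.0) | 2, 5 (3.5) |
| C, patients 17-24 | 2, 5 (3.5) | 3, 6 (4.5) | 1, 4, 7 (4.0) |

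**The plan as intended.** At 8/8/8 every technique has mean phase 4.0 and 8 × (3 + 2 + 2) = 56 phases. The intended balance is exact.

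**Measure 1, for a first-week effect.** A patient's mean for the technique used first takes 1/3 of its weight from phase 1; the other two techniques take none. With a, b and c patients in orders A, B and C and n = a + b + c, the share is (c - a)/(3n) for N minus F and (b - a)/(3n) for O minus F.

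**Measure 2, for a linear trend.** F minus O in mean phase is +0.5 in A, +0.5 in B and -1.0 in C. F minus N is -0.5, +1.0 and -0.5. These are averaged over the patients enrolled.

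| Patients at stop | Phase-1 share, N - F | Phase-1 share, O - F | Mean phase, F - O | Mean phase, F - N |
|---|---|---|---|---|
| 8 | -0.33 | -0.33 | +0.50 | -0.50 |
| 12 | -0.22 | -0.11 | +0.50 | 0 |
| 16 | -0.17 | 0 | +0.50 | +0.25 |
| 20 | -0.07 | 0 | +0.20 | +0.10 |
| 24 | 0 | 0 | 0 | 0 |

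For example, at 12 patients (8 in A, 4 in B) the N - F share is (0 - 8)/36 = -0.22. Between the rows shown, F - N in mean phase is negative up to 11 patients and positive from 13 to 23.

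**The same stops with blocks of three or simple rotation.** At most one order is one patient ahead or behind. The largest phase-1 share gap is 1/(3n): 0.042 at 8, 0.021 at 16, 0.017 at 20, and 0 at 12. The largest mean-phase gap is 1.0/n: 0.125, 0.0625, 0.05 and 0.

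**Size for distress.** The documents give no first-week effect, so I assume an excess of 5 to 20 points on the 0-100 scale, with about one weekly score per phase (five fractions a week assumed). The false no-mask benefit is the excess times the share:

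- stop at 8: 1.7 to 6.7 points
- stop at 12: 1.1 to 4.4
- stop at 16: 0.8 to 3.3
- stop at 20: 0.3 to 1.3

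With blocks or rotation, a stop at 8 gives at most 20/24 = 0.8 points.

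**Size for displacement.** Assume a worsening of 0.1 to 0.5 mm per phase. At 8 patients the bias is 0.5 × drift = 0.05 to 0.25 mm, in favour of open mask and against no mask. At 16 it is 0.05 to 0.25 mm in favour of open mask and 0.025 to 0.125 mm in favour of no mask. The margin in section 10.1 is 2 mm.

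**Learning with all 24 complete.** Assume the extra time for surface scanning decays exponentially, with a time constant of 4 to 26 weeks and even accrual over 45 weeks to a year. The gap between open mask and no mask is then about 0.5% to 1.4% of the starting excess. With an 8-week constant and 45 weeks' accrual, for example, the average remaining excess is 14.2% for open mask and 12.8% for no mask.

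**The case against.** The strongest reply is that the planned study has no phase imbalance at all: at 24 completers every offset is zero. The termination clause in section 2.3 is a general reservation of rights, and section 2.2 lets the duration change, so slow accrual might simply lengthen the study. That stands. The problem is conditional on stopping short, although the protocol itself names poor enrolment as a reason to stop.

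A second reply is that a model with patient, phase and technique terms could adjust for the imbalance. This is estimable once patient 9 is enrolled, but not with 8 or fewer, and at 9 patients it rests on a single patient in the second order. Section 10.2 does not plan such a model.

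Several stronger readings are tempting and are not supported:

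- A reader might infer that early stopping tilts the result towards the new techniques. A first-week rise would favour no mask at every early stop, but open mask only before patient 16. A linear worsening would favour open mask at every early stop, but would work against no mask up to 11 patients and for it only from 13. An improvement over the course would reverse the signs of the linear case.
- A reader might blame consecutive filling for the effect of unreplaced withdrawals. These unbalance any scheme; consecutive filling adds to it only if withdrawal varies over calendar time. Losing four patients from A, B or C shifts F - O in mean phase by -0.10, -0.10 or +0.20, and F - N by +0.10, -0.20 or +0.10, so the tilt can go either way.
- A reader might expect staff learning to distort the completed study. Every patient receives all three techniques by phase 3, so most of it cancels within patient.

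**Conclusion.** The allocation rule leaves the study without phase balance at any stop before patient 24 and ties order completely to calendar time. The imbalances follow exactly from the stated schedules. The resulting bias rests on assumed time effects and scales with them: a few distress points in a study stopped at 8 to 16 patients, and at most about 0.25 mm in displacement. The main exposure is therefore distress (a secondary endpoint) and treatment time (listed under the primary endpoint in section 3.2), and much less the displacement comparison. With all 24 complete, the phase imbalance is zero and the learning bias is about 1% of the starting excess. This is a cheap improvement in robustness, not a flaw that undermines the completed trial.

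**What to change.** In section 5, section 2 and the synopsis, replace the consecutive blocks of eight with allocation of the same three orders in permuted blocks of three (one patient per order in each block), from a list prepared in advance and opened after consent. The total stays at 8 patients per order. If permuted blocks are used, amend the synopsis label "Non randomised clinical interventional study". At minimum, rotate the orders patient by patient (1, 2, 3, 1, 2, 3, and so on).

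The cost is one allocation list and a wording change, with no extra patients or procedures. The downside is that staff run three orders in parallel from the start.

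The change does not cure carry-over imbalance. All three orders follow the same full-open-no cycle, so each technique always follows the same predecessor, however the orders are allocated.
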